10 SAFETY REPORTING

10.1 Time Period for Active Monitoring of Safety Events

The "active monitoring" of all safety events experienced by trial participants will be from randomisation until 48 hours after visit 9.

Any additional information on selected adverse events related to the initial challenges, will be captured in the Challenge Form (see sections 8.4.1.2 and 8.4.1.3). Expected adverse events during the challenges will not be included in the adverse events log, but rather in the challenge logs.

Any safety events occurring *after* the end the active monitoring period that meet the definition of **serious** (see section 10.3) must continue to be reported by sites to the LCTC in accordance with the timeframes and procedures described in section 10.9.

Upon becoming aware of a serious adverse event (SAE/Related SAE/RUSAE), the investigator or other delegated member of the site team must report this to the LCTC **within 24 hours**.

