8.7.4.2 VISIT 9 (DBPCFC Day 2)

Visit 9 will be conducted 1-4 weeks from visit 8. This visit entails Day 2 of the DBPCFC to CM, as per the trial DBPCFC SOPs. Participants will be monitored by a delegated clinician, supported by delegated nurse(s), and will remain in the department for up to 8 hours, as appropriate. In rare cases and if they experience severe anaphylaxis, they may need to be hospitalised overnight, as per the clinical judgment of the clinician.

- 1. Confirm continuation of participation.
- 2. Physical Examination, current medical history & vital signs: Weight, length, EASI Score & history of wheeze. The following will be confirmed to be normal and a statement to this effect recorded in the medical notes: general physical examination with chest auscultation, Peripheral arterial pulse, heart rate, systolic and diastolic blood pressure, respiratory rate, and oxygen saturation.
- 3. Collect diary from previous visit: Collect completed diary pages from previous visit and review. Any new AEs will be recorded in the participant's medical notes and on the AE Log and any previous AEs will be followed-up and marked as resolved if appropriate.
- 4. Demographics & review of medical history and diet: Details of any personal history of disease with focus on asthma, wheeze, urticaria and angioedema, atopic dermatitis, food allergies, and drug allergies. Concomitant medication
- 5. Challenge Day 2: Will be conducted as per the trial DBPCFC SOPs. Results of the DBPCFC must be recorded in the **participant's medical notes**. Unblinding of the challenge will take place as per the SOPs.
- 6. Record AEs: Any AEs occurring from this visit must be recorded in the participant's medical notes and on the AE Log (see section 10).
 - DBPCFC negative: Participants with a negative result to both days of the DBPCFC will be provided with advice for re-introduction of milk into the diet.
 - DBPCFC positive: Participants with a positive result to either day of the DBPCFC should be provided with clinical advice for ongoing CMA management at the clinician's discretion.
- 7. Collect any unused tins from parents: Collect any returned tins for destruction. Record returns and destruction in the appropriate accountability log.

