10.2 Terms and Definitions

Table 1: Terms and Definitions of Safety Events

Adverse Event (AE)	Any untoward medical occurrence, unintended disease or injury or any untoward clinical signs (including an abnormal laboratory finding) in subjects, users, or other persons whether or not related to the investigational product.
Related Adverse	An AE which resulted from administration of any of the research procedures
Event (Related AE)	- i.e. assessed as "probably", "possibly" or "almost certainly" related to the
	trial procedures (see section 10.5).
Serious Adverse	An adverse event which meets the definition of "serious" (see section 10.3).
Event (SAE)	
Related Serious	An adverse event which meets the definition of "serious" (see section 10.3).
Adverse Event	A SAE which is assessed to be "probably", "possibly" or "almost certainly"
(Related SAE)	related to the trial procedures (see section 10.5).
Related Unexpected	A Related SAE which is not expected, i.e. not consistent with the known
Serious Adverse	effects of the trial procedures (see section 10.5).
Event (RUSAE)	

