10.6.1 Reference Safety Information (RSI)

The RSI in DREAM is detailed in Table 4: Expected Events

Table 4: Expected Events

Event	
Anaphylaxis	
Urticaria	
Exacerbation of eczema	
Allergic reaction	
Acute bronchospasm (asthma)	

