10.7 Notes on Adverse Event Inclusions and Exclusions

The following events must be recorded for the purposes of the trial:

- An exacerbation of a pre-existing illness.
- An increase in frequency or intensity of a pre-existing episodic event/condition.
- A condition (even though it may have been present prior to the start of the trial) detected after trial treatment.
- Continuous persistent disease or symptoms present at baseline that worsens following the administration of the study/trial treatment.
- Laboratory abnormalities that require clinical intervention or further investigation (unless they are associated with an already reported clinical event).
- Abnormalities in physiological testing or physical examination that require further investigation or clinical intervention.
- Injury or accidents.

Do not record:

- Medical or surgical procedures the condition which leads to the procedure is the adverse event.
- Pre-existing disease or conditions present before treatment that do not worsen.
- Situations where an untoward medical occurrence has occurred e.g. cosmetic elective surgery*.
- Overdose of medication without signs or symptoms**
- The disease being treated or associated symptoms/signs unless more severe than expected for the patient's condition

* Elective surgery is cited here as example of an event that is not reportable as an AE.

[figure not shown]
** See also section 10.12.1. If overdose occurred with resulting signs and symptoms that met the protocol criteria for AEs or /SAEs/ then they should be reported accordingly. This bullet is to note that though overdose of medication without signs or symptoms may be excluded from AE reporting this may still require investigation to ensure the protocol and regulatory requirements are met e.g. for IMP management and administration to ensure participant safety.

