10.9.1 Flowchart for Reporting Requirements of Adverse Events

10.9.2 Reporting Safety Events

All safety events (whether or not assessed as serious / related / expected) should be recorded on an AE form; multiple events can be recorded on one form.

Safety events that are assessed as "serious" must **also** be recorded in more detail on an SAE Form; a single form is used for each individual event (i.e. a single diagnosis), though multiple symptoms can be recorded. Each SAE should have a corresponding record on the participant's AE form.

Additional information should be provided on a follow-up form and sent to LCTC within 5 days if the serious event has not resolved at the time of the report.

SAE Forms collect data regarding the nature of event, date of onset, severity, corrective therapies given, outcome and causality; all serious events reported to LCTC will be reviewed by the CI or authorised delegate and assessed for causality and expectedness.

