11.3 Sample Size calculation

We have set high inclusion thresholds for SPTs/IgE, to recruit infants with a low chance to 'spontaneously' outgrow CMA (that is, to outgrow CMA while they are under normal care-eHF feeding, as is the case for our control group). Therefore, although population-based studies report a high rate of up to 75% spontaneous CMA resolution [5, 65, 66], in patients meeting our strict criteria only 37% developed tolerance by age four in one study [29] and only 20-30% by 3 years of age in three other studies [30, 67, 68]. We therefore expect spontaneous resolution (for the 'normal care' group) to be ~30% and allowed for 35% (closest to the highest reported) to ensure that the study will be sufficiently powered even in the worst-case scenario.

Regarding the expected resolution rate for the active intervention (pHF) group, to date there is no study using pHF for free feeding and there is no evidence for an expected rate. Although CM OIT has a success rate of 65%-90% [36-42] our study differs from CM OIT in that we are not giving normal CM but a less allergenic form (and therefore one would expect lower rates of CMA resolution in our trial due to exposure to less CM proteins); on the other hand, our trial also differs from CM OIT in that we are not giving the OIT product in small doses but in large quantities (freely), and therefore one would expect higher rates of resolution in our trial due to exposure to more protein. In any case, to power our study reliably we assume that the resolution rate for the intervention group should be at the lower end of the reported rates for CM OIT (65%). To ensure that the study will be sufficiently powered even in the worst-case scenario, we calculated the power on an expected 60% size effect for the pHF group. Indeed, a study where processed CM (baked milk) was used for desensitisation returned a size effect of 60% [53], further indicating that this would be an appropriate effect size.

A two-group chi-squared test with a 0.05 two-sided significance level will have 90% power to detect the difference between a proportion of 0.35 in the eHF group and a proportion of 0.60 in the pHF group (odds ratio of 2.786) when the sample size in each group is 82. Allowing for 20% attrition, a total of 206 patients will be randomised.

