11.5 Analysis Plan

The trial will be analysed using the International Conference on Harmonisation E9 guidelines and reported using the 'Consolidation Standard of Reporting Trials' (CONSORT) guidelines.

The analyses of primary and secondary outcomes will use the principle of intention to treat, based on all the randomised participants, as far as is practically possible. A p-value of 0.05 or less will be used to declare statistical significance for all analyses and results will be presented with 95% confidence intervals. Baseline characteristics will be presented but no comparisons will be undertaken, rather the clinical importance of any imbalance will be noted.

Binary data (including the primary outcome of the proportion of patients who are no longer allergic to CM protein) will be reported in terms of relative risk and analysed using logistic regression, adjusted for the stratification factors (site and initial tolerance to pHF). There will be a secondary analysis of the primary outcome using a chi-squared test for consistency with the sample size calculation. There will also be two subgroup analyses of the primary outcome, the first will include patients who initially tolerate pHF and the second will include patients who did not initially tolerate pHF.

Continuous data will be presented as means and standard deviations and analysed using two-sample t-tests (if data is skewed, medians and ranges will be presented, and analysis will be by Mann Whitney U tests). All related AEs and serious adverse events SAEs reported by the clinical investigator will be presented, identified by treatment group, but no formal comparisons will be made across the treatment groups.

Missing data will be monitored, and strategies developed to minimise its occurrence, however as much data as possible will be collected about the reasons for missing data and this will be used to inform the handling of missing data.

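### Section 10.1 does not say whether its challenge carve-out covers the V8/V9 DBPCFC, so the by-arm adverse event table may mix primary-outcome failures with the safety of feeding

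*Protocol*

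**What the plan says.** Four parts of the protocol bear on where a reaction to milk during the DBPCFC is recorded.

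- **Section 10.1** sets active monitoring from randomisation to 48 hours after V9. It then has a sentence on the initial challenges, cross-referring to 8.4.1.2 and 8.4.1.3 (V2 and V3), followed by: "Expected adverse events during the challenges will not be included in the adverse events log, but rather in the challenge logs".
- **Sections 8.7.4.1 and 8.7.4.2** (V8 and V9) each say: "Any AEs occurring from this visit must be recorded in the participant's medical notes and on the AE Log", with a pointer to section 10.
- **Section 10.9.2** says: "All safety events (whether or not assessed as serious / related / expected) should be recorded on an AE form".
- **Section 10.7** lists, among things not to record: "The disease being treated or associated symptoms/signs unless more severe than expected" for the patient's condition.

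Three further provisions decide what follows.

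- **Section 10.6.1**: "The RSI in DREAM is detailed in Table 4: Expected Events". That table lists anaphylaxis, urticaria, exacerbation of eczema, allergic reaction and acute bronchospasm.
- **Section 10.2** defines a related AE as "An AE which resulted from administration of any of the research procedures".
- **Section 11.5**: "All related AEs and serious adverse events SAEs reported by the clinical investigator will be presented, identified by treatment group", without formal comparison.

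Secondary objective 1 (section 3.3.2) is the safety of feeding with either formula.

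**The concern.** A reaction on the milk day of the DBPCFC is caused by the test meal, not by the formula fed over the preceding year. It is also what section 8.8.1 uses to classify the infant as still allergic, so it is failure on the primary outcome. If such reactions enter the related-AE table, the arm with less tolerance collects more of them. The table then reflects efficacy as well as harm, and tilts towards whichever formula works better. If instead some sites log these reactions and others keep them on the challenge log, the counts mix two rules and no later analysis can separate them cleanly. The recorded events also go yearly to the ethics committee and the IDSMC (section 10.12).

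A smaller difficulty adds to this. Section 10.1 makes log entry depend on whether an event is expected, but section 10.6 gives that judgement to the Chief Investigator and does not ask the reporting site to make it.

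**Working it through.** **Step 1. One event under each reading.** Take urticaria during the V8 milk challenge. It is in Table 4, falls inside the monitoring period, and results from a research procedure.

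- *Broad reading of 10.1 (all challenges).* 10.1 keeps it off the AE log and 10.7 can be read the same way. 10.9.2 requires it on an AE form even if expected, and the V8 item sends it to the AE log. The rules conflict.
- *Narrow reading of 10.1 (V2 and V3 only).* 8.7.4.1 and 10.9.2 agree that it goes on the AE log. It is a related AE by 10.2 and is presented by arm under 11.5. The 10.7 bullet remains in tension, because milk allergy is the disease being treated.

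Neither reading gives both a single recording rule and a table confined to feeding and OIT.

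**Step 2. Confirm the design rates.** Section 11.3 assumes "a proportion of 0.35 in the eHF group and a proportion of 0.60 in the pHF group", two-sided alpha 0.05, 90% power, 82 per group and 20% attrition.

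n per arm = [z(0.975) × √(2 × 0.475 × 0.525) + z(0.90) × √(0.35 × 0.65 + 0.60 × 0.40)]² / 0.25²

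= [1.960 × 0.7062 + 1.2816 × 0.6837]² / 0.0625 = 81.7, rounded up to 82.

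Power at 82 per arm is 0.901. 82 / 0.80 = 102.5, rounded up to 103 per arm, 206 in total. The protocol's figures reproduce.

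**Step 3. Number of DBPCFC reactors.** Assume every infant who is not tolerant reacts.

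- eHF: 82 × (1 − 0.35) = 53.3
- pHF: 82 × (1 − 0.60) = 32.8
- Gap: 82 × 0.25 = 20.5 infants (25 percentage points)

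**Step 4. Dependence on the treatment effect.**

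- pHF tolerance 50%: 82 × 0.50 = 41.0 pHF reactors, gap 53.3 − 41.0 = 12.3.
- pHF tolerance 35% (no effect): gap 0.
- Design rates with all 103 per arm assessed: 103 × 0.65 = 67.0 and 103 × 0.40 = 41.2, gap 25.8.

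**The case against.** The strongest reply is that the conflict largely disappears on the natural reading.

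- The sentence in 10.1 follows one about the initial challenges, which cross-refers only to the V2 and V3 sections.
- The schedule in section 7 marks adverse event assessment at V8 and V9 but not at V2 or V3.
- The carve-out is not idle on that reading. pHF-tolerant infants are randomised at V3, after that day's challenge, and late symptoms are sought for 48 hours, so V3 reactions can run into the monitoring period.
- The V8 and V9 items defer to section 10, so they are not independent rules.
- The 10.7 bullet is generic and does not mention challenges.
- How challenge reactions are tabulated is commonly left to the SAP, and the DBPCFC SOP may settle site recording. Neither document is at hand.

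Most of this stands, and the narrow reading is the better one. It settles where the event is logged but creates the other problem: DBPCFC reactions then meet the 10.2 definition and 11.5 presents them by arm. It also leaves 10.7 unresolved. An SAP can separate challenge reactions cleanly only if sites recorded them under one rule, and the protocol sets that rule.

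A reader might go further and infer that the table would reverse the safety ranking. For example, suppose feeding-related AE rates of 10% under eHF and 25% under pHF, independent of the challenge result. The share of infants with any related AE would then be 1 − 0.90 × 0.35 = 68.5% under eHF and 1 − 0.75 × 0.60 = 55.0% under pHF, so pHF would look 13.5 points better instead of 15 points worse. The protocol does not support this as a finding. It gives no feeding AE rates, says nothing about their dependence on the challenge result, and does not specify a per-infant summary of any related AE.

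**Conclusion.** The point holds as a minor drafting fault with a limited consequence. Section 10.1 does not name the challenges it covers. The broad reading gives contradictory instructions. The better-supported narrow reading puts primary-outcome failures into the table that serves the safety-of-feeding objective.

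The size is at most about 53 eHF and 33 pHF infants, a gap of about 20. This assumes the protocol's tolerance rates, 82 infants assessed per arm, and a reaction in every non-tolerant infant. The last is an upper limit, since section 8.8.1 also has an inconclusive class that includes unfinished challenges. The gap shrinks with the treatment effect and is zero without one.

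It would be too strong to say that the safety conclusion is shown to be wrong or reversed. The table is descriptive, a reader will also have the DBPCFC result itself as the primary outcome, and the SAP or SOPs may already keep these events apart. The primary outcome, alpha, power and the 24-hour reporting of SAEs are unaffected.

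**What to change.** - **10.1**: name the challenges covered (V2, V3, V8 and V9) and state one rule. Expected challenge reactions, and late symptoms within 48 hours judged associated with the challenge, go on the challenge log. SAEs are reported regardless. All other AEs go on the AE log. Define expected here as an event type in Table 4, so that sites can apply the rule without the judgement that 10.6 reserves to the Chief Investigator.
- **10.9.2 and the Record AEs items in 8.7.4.1 and 8.7.4.2**: add an exception referring to 10.1.
- **10.7**: state that the last do-not-record bullet does not exclude reactions to the trial formula.
- **11.5**: present DBPCFC reactions by arm, separately from feeding and OIT adverse events.

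The cost is wording in six sections and a note to sites. No visit or contact is added. Section 10.1 already provides for challenge logs, so no new form should be needed.

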10.2 Terms and Definitions

Table 1: Terms and Definitions of Safety Events

Adverse Event (AE)	Any untoward medical occurrence, unintended disease or injury or any untoward clinical signs (including an abnormal laboratory finding) in subjects, users, or other persons whether or not related to the investigational product.
Related Adverse	An AE which resulted from administration of any of the research procedures
Event (Related AE)	- i.e. assessed as "probably", "possibly" or "almost certainly" related to the
	trial procedures (see section 10.5).
Serious Adverse	An adverse event which meets the definition of "serious" (see section 10.3).
Event (SAE)	
Related Serious	An adverse event which meets the definition of "serious" (see section 10.3).
Adverse Event	A SAE which is assessed to be "probably", "possibly" or "almost certainly"
(Related SAE)	related to the trial procedures (see section 10.5).
Related Unexpected	A Related SAE which is not expected, i.e. not consistent with the known
Serious Adverse	effects of the trial procedures (see section 10.5).
Event (RUSAE)	

10.3 Assessment of Seriousness

The assessment of seriousness of safety events should be performed by an appropriately delegated, medically qualified member of the site research team.

A safety event (whether or not assessed as related to the trial) is assessed as serious if it:

- Results in death;
- Is life-threatening (i.e. the investigator considers the event places the subject at immediate risk of death from the experience as it occurred (this does not include an adverse experience that, had it occurred in a more severe form, might have cause death);

- Requires hospitalisation or prolongation of existing hospitalisation (hospitalisation is defined as an inpatient admission, regardless of length of stay, even if the hospitalisation is a precautionary measure for continued observation);
- Results in persistent or significant disability or incapacity (substantial disruption of one's ability to conduct normal life functions);
- Consists of a congenital anomaly or birth defect (in offspring of trial participants, or their partners, regardless of time of diagnosis), or
- Is otherwise considered medically significant by the investigator.

10.4 Severity of Adverse Events

All adverse events should be assessed for severity. The assignment of the severity/grading should be made by the investigator responsible for the care of the participant using the definitions in the table below:

Table 2: Definitions of Severity Grading

Mild	Does not interfere with routine activities
Moderate	Interferes with routine activities
Severe	Impossible to perform routine activities

N.B. A distinction is drawn between **serious** and **severe** AEs. Severity is a measure of intensity whereas seriousness is defined using the criteria in section 10.3. Hence, a severe AE need not necessarily be a Serious Adverse Event.

10.5 Relationship to Trial Treatment

The assessment of causality should be made by the investigator responsible for the care of the participant using the definitions in *Error! Reference source not found.*.

Unrelated	There is no evidence of any causal relationship.
	N.B. An alternative cause for the AE should be given
Unlikely	There is little evidence to suggest there is a causal relationship (e.g. the event
	did not occur within a reasonable time after administration of the trial
	medication). There is another reasonable explanation for the event (e.g. the
	participant's clinical condition, other concomitant treatment).
Possibly	There is some evidence to suggest a causal relationship (e.g. because the
	event occurs within a reasonable time after administration of the trial
	medication). However, the influence of other factors may have contributed to
	the event (e.g. the participant's clinical condition, other concomitant
	treatments).
Probably	There is evidence to suggest a causal relationship and the influence of other
	factors is unlikely.
Almost certainly	There is clear evidence to suggest a causal relationship and other possible
	contributing factors can be ruled out.

Table 3: Definitions of Causality

If any doubt about the causality exists, the local investigator should inform the study coordination centre who will notify the CI. In the case of discrepant views on causality between the investigator and others,

the opinion of the treating investigator will never be downgraded, and the REC will be informed of both points of view.

